10.4.1 Similarity Acceptance

Using GLM procedures in SAS[®], ANOVA will be performed on untransformed $T_{\max,E}$ and ln-transformed $AUEC_{0-t}$, $AUEC_{0-7}$, $AUEC_{0-14}$, $AUEC_{14-t}$, $AUEC_{14-35}$, and E_{\max} at the alpha level of 0.05. Factors incorporated in the model will include: Vaccine, IG, and Vaccine*IG. Vaccine, IG, and Vaccine*IG will be tested against the residual mean square error. In the case of a non-statistically significant Vaccine*IG interaction term, the analysis will be rerun excluding this term from the ANOVA model in order to obtain ratios and confidence intervals where appropriate. In the case of statistically significant Vaccine*IG interaction term, the analysis will be rerun for each vaccine separately. All sums of squares (Types I, II, III and IV) will be reported. Probability (p) values will be derived from Type III sums of squares. Coefficients of variation (CV%) will be estimated.

Based on pairwise comparisons of the ln-transformed $AUEC_{0-t}$, $AUEC_{14-t}$, and E_{\max} data, the ratio (RIG/SYN023) of the geometric least-squares means, calculated according to the formula “ $e^{(X-Y)} * 100$ ”, as well as the corresponding 90% geometric confidence intervals will be determined.

For $AUEC_{14-t}$, a statistically significant Vaccine*Conmed interaction term will be interpreted as a possible interference of RIG or SYN023 on the vaccines. In this case, each vaccine will be investigated separately.

Additional analyses may be performed.

Criteria for Similarity

Considering PP population, the 90% geometric confidence intervals of the ratio (RIG/SYN023) of least-squares means from the ANOVA of the ln-transformed $AUEC_{0-t}$ must be within 80.00% to 125.00%.

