### Criteria for Pharmacodynamic Similarity Acceptance

Rabies Virus Neutralizing Activity plotted against time will be created. Pharmacodynamic parameters for SYN023 mAb will be estimated using non-compartmental analysis. Cmax, Tmax, AUC0-last, AUC0-inf will be calculated. For the comparison of RIG to SYN023 with RVi and RVa vaccines: The 90% confidence intervals for the ratio of geometric means (RIG/SYN023) must be 80% to 125%. An ANOVA of the ln-transformed AUC0-inf will be run to determine the 90% confidence interval on the difference between treatments. The confidence interval limits derived on the log scale will be back-transformed to the raw AUC scale for comparison to the acceptance criteria.

To investigate any interference of SYN023 to the immune response generated by the vaccine, a non-inferiority test of the AUC14-last between RIG and SYN023 for each vaccine can be performed. The one-sided 90% confidence interval derived on the log transformed AUC from an ANOVA would be compared to the lower acceptance criterion of 80%.

Additionally, a non-inferiority test of the level of RVNA between RIG and SYN023 for each vaccine at selected time points, such as 14 or 28 days, can be performed using a Wilcoxon rank sum approach with a non-inferiority of 10% of the level associated with RIG. Pharmacodynamic efficacy will be defined as RVNA measured above 0.5 IU/mL with RVi and RVa for the duration of the trial and no more than 10% lower for SYN023 compared to RIG at any time point through Study Day 35.

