### **7.7 Sample Size Considerations**

The sample size for this Phase 2 study was selected based on requirement to consider noninferiority of the efficacy parameter, RVNA. The power analysis was performed in SAS 9.2 using the power procedure for noninferiority testing under the assumption of the sample size of 40 per group and likely margin corresponding to SYN023 being no less than 10% lower than RIG. Based on earlier studies, the mean RVNA for 0.3 mg/kg SYN023 of 20 with CV of 15-25% are reasonable. For assumed underlying differences of 0 to 1 IU/mL, there is over 80% to conclude non-inferiority of RVNA level at a specified time point. The sample size of 40 per treatment group should be sufficient to address the efficacy objectives of the study.

The assumptions that a difference of 2 or less is considered unimportant (the approximate mean value for 0.3mg/kg SYN023 of 20 was used), with the range in mean difference from -1 to 1, standard deviation of 3 and power of 0.8, the required sample size of 29 is needed to declare that the new treatment (SYN023) is not more tolerably inferior to the previous treatment (RIG). Also, the power analysis was performed for the sample size of 40, standard deviation 3 and the mean difference of 2. This resulted in the power of 0.838. The above results from the sample size and power analysis showed that the sample size of 40 should be sufficiently powered for this study.

Also, a power analysis for non-inferiority of the AUCs was performed using “PowerTOST”, an R CRAN package run under Rstudio version 0.99.491. Under the assumption of a lower non-inferiority bound of 0.9 (corresponding to SYN023 being no less than 10% lower than RIG), the selected sample size of 40 per group would provide over 80% power assuming a CV of 10-20%.

If no SAEs are observed among subjects in each dose group and the 40 subjects in the 3 dose groups combined, the one-sided exact upper 95% confidence bounds on the rate of SAE occurrence will be 45% and 18%, respectively.

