3.1 General Design

This is a Phase 2 single site, randomized, blinded comparison of the immunogenicity of RVi and RVa when administered with RIG or SYN023. Up to 160 subjects are planned to be included in this study. Subjects will be randomized into one of four treatments with a ratio of 1:1:1:1 (40 subjects per treatment). All injections will be given intramuscularly.

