10.4.2 RIG vs. SYN023 Comparison by Timepoint

Using GLM procedures in SAS[®], ANOVA will be performed separately on ln-transformed RVNA at Day 1, Day 3, Day 7, Day 14, Day 28, Day 35, Day 42, Day 84, and Day 112 at the alpha level of 0.05. Factors incorporated in the model will include: Vaccine, Conmed, and Vaccine*Conmed. Vaccine, Conmed, and Vaccine*Conmed will be tested against the residual mean square error. In the case of a non-statistically significant Vaccine*Conmed interaction term, the analysis will be rerun excluding this term from the ANOVA model in order to obtain ratios and confidence intervals where appropriate. In the case of statistically significant Vaccine*Conmed interaction term, the analysis will be rerun for each vaccine separately. All sums of squares (Types I, II, III and IV) will be reported. Probability (p) values will be derived from Type III sums of squares. Coefficients of variation (CV%) will be estimated.

Based on pairwise comparisons of the ln-transformed Day 1, Day 3, Day 7, Day 14, Day 28, Day 35, Day 42, Day 84, and Day 112 data, the ratio (RIG/SYN023) of the geometric least-squares means, calculated according to the formula “ $e^{(X-Y)} * 100$ ”, as well as the corresponding 90% and 95% geometric confidence intervals will be determined.

Additional analyses may be performed.

11. Immunogenicity: Anti-SYN023 Antibodies Analyses

Shells for all summary descriptive statistic tables and listings referred to in this section are displayed in a separate document; the shells may be revised as they are presented to illustrate the general layout of data to be included in the final report.

Immunogenicity analyses will be performed on PP population. No inferential analysis will be done.

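### SAP 10.4.1 gives each vaccine its own similarity interval only after a significant interaction test; otherwise one pooled interval decides, and it can cover a vaccine sitting at the limit

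*SAP*

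**What the plan says.** The design is a 2x2 factorial (vaccine RVi or RVa, antibody RIG or SYN023). SAP 3.1: "Subjects will be randomized into one of four treatments with a ratio of 1:1:1:1 (40 subjects per treatment").

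SAP 10.4.1 fits an ANOVA to ln-transformed AUEC0-t and other parameters with Vaccine, IG and Vaccine*IG, "at the alpha level of 0.05". The next step depends on the interaction test:

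- Not significant: "In the case of a non-statistically significant Vaccine*IG interaction term, the analysis will be rerun excluding this term from the ANOVA model". The ratio comes from the reduced model.
- Significant: each vaccine is analysed on its own.

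For the ratios, the "corresponding 90% geometric confidence intervals will be determined". The similarity criterion is that the 90% interval for RIG/SYN023 on AUEC0-t "must be within 80.00% to 125.00" percent. It does not say that each vaccine must meet this. For AUEC14-t, a significant interaction is read as possible interference, and only then is each vaccine investigated separately.

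SAP 10.4.2 uses the same pre-test at nine time points; after a significant interaction, "the analysis will be rerun for each vaccine separately". It sets no acceptance limit.

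Protocol 7.3 names both vaccines for the 80-125% comparison without saying whether they are pooled. Its further non-inferiority test on AUC from Day 14 "between RIG and SYN023 for each vaccine can be performed", and the test on RVNA level at selected days is also framed by vaccine. SAP section 4, on changes from the protocol, does not mention pooling.

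**The concern.** The Rationale in the protocol's Study Abstract asks whether SYN023 inhibits the response to two licensed vaccines. Interference could affect one and not the other, or affect them to different degrees. Under the SAP rule, a formal answer for each vaccine exists only if a preliminary test finds the vaccines different. If it does not, the stronger vaccine's result is averaged with the weaker one's, and the average is compared with the limits.

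Failing to detect an interaction does not establish that the two ratios are equal, and an interval chosen after such a pre-test does not keep its nominal error for either vaccine. At stake is a similarity conclusion that readers apply to both vaccines when one of them has a true RIG/SYN023 ratio of 1.25, the edge of what the plan accepts.

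**Working it through.** **The plan's own figures.** Protocol 7.7 gives 29 per group for 80% power (margin 2, SD 3). The exact t calculation returns 29 at one-sided 0.05 with a true difference of 0. It also gives power 0.838 for 40 per group, SD 3, difference 2; this reproduces at two-sided 0.05. For AUC it says "the selected sample size of 40 per group would provide over 80% power assuming a CV of 10-20" percent, with a bound of 0.9. All of these are two-group comparisons. Neither the interaction test nor the 80-125% criterion has a stated power.

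**Inputs.** 40 per cell (SAP 3.1); interaction test at two-sided 0.05, 90% CI and limits 0.80-1.25 (SAP 10.4.1); AUC CV 10-20% (Protocol 7.7). My assumptions are log-normal data with equal variance, one vaccine truly at 1.25, and the other vaccine's ratio varied.

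**Formulas.** The log-scale SD is σ = √ln(1 + CV²), so CV 20% gives σ = √ln 1.04 = 0.198.

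- Per-vaccine log ratio: SE = σ√(2/40).
- Interaction (difference of two log ratios): SE = σ√(4/40) = 0.0626 at CV 20%.
- Pooled log ratio: SE = σ√(1/40) = 0.0313 at CV 20%.

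**Two cases by hand at CV 20%.**

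- Ratios 1.25 and 1.00: gap ln 1.25 = 0.223; 0.223/0.0626 = 3.56; interaction power 94%. The rule usually catches this.
- Ratios 1.25 and 1.10: gap ln(1.25/1.10) = 0.128; 0.128/0.0626 = 2.04; power 53%. The true pooled ratio is √(1.25 × 1.10) = 1.173, log 0.159. The 90% half-width is about 1.655 × 0.0313 = 0.052, so the expected upper limit is exp(0.211) = 1.235, inside 1.25. When the interaction is missed, the pooled interval will often pass.

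**Simulation of the full rule** (400,000 trials per scenario). Declaration risk is the chance that the vaccine at 1.25 is covered by a similarity declaration: the pooled interval passes after a non-significant test, or its own interval passes after a significant one. Nominal is 5%.

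| Other vaccine | CV | Interaction power | Declaration risk |
|---|---|---|---|
| 1.00 | 10% | 100% | 5.0% |
| 1.00 | 15% | 99.7% | 5.1% |
| 1.00 | 20% | 94% | 8.5% |
| 1.05 | 15% | 96% | 7.5% |
| 1.05 | 20% | 79% | 19% |
| 1.10 | 10% | 98% | 6% |
| 1.10 | 15% | 77% | 21% |
| 1.10 | 20% | 53% | 31% |
| 1.15 | 10% | 75% | 22% |
| 1.15 | 15% | 42% | 32% |
| 1.15 | 20% | 26% | 28% |

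**If the AUEC CV exceeds planning** (an assumption), with the other vaccine at 1.00: power is 81%, 67% and 44% at CV 25%, 30% and 40%, and the risk is 18%, 26% and 32%. Such CVs are not excluded. Protocol 7.7 uses 15-25% for RVNA levels. In Protocol Table 1.5-1 at 0.3 mg/kg, the ± value divided by the mean runs from 0.41/3.78 = 11% (Day 14) to 0.93/1.82 = 51% (Day 35), though the table does not say what the ± is.

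Judged on its own 90% CI, a vaccine at 1.25 passes in at most 5% of trials at every CV tried.

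**The case against.** The strongest reply is that the rule works where the plan expects to be. For 1.25 against 1.00 at CV 10-20%, interaction power is 94-100% and the risk is 5-8.5%. That stands. A reader might infer that the interaction test is underpowered in general; the planning figures do not support that. The problem needs either a smaller gap between the vaccines or a CV above planning.

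Four other stronger readings also fail.

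- *The SAP breaks a protocol requirement for per-vaccine similarity.* The by-vaccine wording in Protocol 7.3 belongs to optional non-inferiority tests. For the 80-125% criterion the protocol is silent on pooling, so the text is ambiguous and not contradictory.
- *Nothing is reported by vaccine.* SAP 10.4 gives descriptive statistics, including geometric means, for each of the four treatments, so point ratios can be worked out. What is missing is a per-vaccine ratio with its confidence interval.
- *The SAP claims that the pooled interval proves similarity for each vaccine.* It does not say so. The pooled interval is a legitimate estimate of the average ratio. Applying it to each vaccine is an inference from the trial's rationale, which the SAP does nothing to prevent.
- *SAP 10.4.2 carries the same false-declaration risk.* It has no acceptance limit, so no similarity declaration arises there.

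It is also fair to say that a per-vaccine criterion becomes hard to meet at high CVs, which is where pooling helps most.

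**Conclusion.** The concern holds in a conditional form. SAP 10.4.1 lets a non-significant interaction test remove the only inferential result for each vaccine, and one pooled interval then decides similarity. With one vaccine at 1.25, the chance that it is covered by a similarity declaration stays near nominal if the other vaccine is at 1.00 and the CV is as planned. It rises to about four to six times nominal inside the planned CV range when the other vaccine is moderately below the limit; 32% is the highest value found.

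These figures assume log-normal data, equal variances and 40 evaluable subjects in every cell. The analysis set is per-protocol and no dropout allowance is stated, so 40 is the most favourable cell size and interaction power would be lower with fewer. The other vaccine's true ratio is unknown, so the results are a range over scenarios and not a forecast. This is a worthwhile, inexpensive correction; it does not invalidate the pooled estimate.

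**What to change.** In SAP 10.4.1, keep Vaccine*IG in the model whatever its p-value. Always report the RIG/SYN023 ratio and 90% CI for each vaccine from its least-squares means, for AUEC0-t, AUEC14-t and Emax, with the pooled ratio alongside. State similarity on AUEC0-t for a vaccine only if that vaccine's own interval lies within 80.00-125.00%. Report the interaction test as information, not as a gate. In SAP 10.4.2, give the per-vaccine ratios and intervals as well, for consistency only.

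The work is a change of wording and two contrasts from a model already fitted. The statistical cost is width: √(2/40) against √(1/40), so per-vaccine intervals are about √2 = 1.4 times wider. With both true ratios at 1.00, the chance that both vaccines pass is:

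| CV | Both pass |
|---|---|
| 20% or less | at least 99.8% |
| 25% | 97% |
| 30% | 84% |
| 40% | 41% |
| 50% | 12% |

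These come from separate fits by vaccine; taking the residual from the full model changes them by about one percentage point at most. At the planning CVs the change is nearly free. If the CV turns out much higher, a per-vaccine conclusion may be out of reach, and the pooled ratio remains available, labelled as an average over vaccines.

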3.4 Subject Withdrawal and Replacement

Subjects were advised that they were free to withdraw from the study at any time. Over the course of the study, the Sponsor and Investigator or a delegate had the right to withdraw any subject from the study for one of the reasons described below; subject withdrawal will be done in accordance with inVentiv's SOP:

- Safety reason;
- non-compliance with protocol requirements;
- significant protocol deviation;

Subjects who withdraw or are withdrawn from the study after dosing will not be systematically replaced. Subjects who fail to complete the study through Study Day 28 may be replaced at the discretion of the sponsor.

4. Changes From the Protocol

For efficacy/PD analyses, AUC_{0-last} was replaced by $AUEC_{0-t}$, $AUC_{14-last}$ was replaced by $AUEC_{14-t}$, C_{max} was replaced by E_{max} , and T_{max} was replaced by $T_{max,E}$. This is standard nomenclature for such efficacy/PD parameters.

AUC_{0-inf} was removed from Efficacy/PD analyses because elimination phase cannot be calculated for rabies virus neutralizing activity (RVNA).

5. Primary and Secondary Parameters

The primary parameters will be $AUEC_{0-t}$ calculated on RVNA measured above 0.5 IU/mL. All other PD parameters will be regarded as secondary parameters (refer to Sections 10).

The safety, immunology and PK parameters will be regarded as secondary (refer to Sections 9, 11, and 12).

6. Analysis Populations

The analysis of safety and tolerability parameters will be based on the safety population detailed in Section 6.1 below. The analysis of immunogenicity (anti-SYN023 antibodies), PK, and PD parameters will be based on the Per-Protocol population detailed in Section 6.2 below.

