12.4 Statistical Analyses

No statistical analysis is planned on samples obtained from subjects who received Treatment A (RVi + RIG) and Treatment B (RVa + RIG), but any cases of detectable and quantifiable levels observed in these subjects (for those who were analyzed) will be addressed descriptively in the PK report.

For Treatment C (RVi + SYN023) and Treatment D (RVa + SYN023), individual and mean serum concentration versus time curves will be presented using linear and semi-log scales for SYN023. Listings and descriptive statistics (number of observations, arithmetic mean, SD, coefficient of variation [CV%], median, Min, Max, and geometric mean) of the concentrations versus time as well as all PK parameters will be provided for each treatment.

Only descriptive statistics will be used to compare Treatment C and Treatment D.

A table and figures (individual and mean versus time curves) presenting RVNA on SYN023 concentrations ratios over time will be provided. For a given scheduled timepoint, the ratio will be defined as

$$\text{Ratio} = \frac{\text{RVNA}}{\text{CTB011 concentration} + \text{CTB012 concentration}}$$

No attempt will be made to extrapolate or interpolate to correct any concentrations in case of time deviations for ratios calculation. Results will be presented using scheduled times.

Additional analyses may be performed.

13. Data Handling

Safety, tolerability, immunogenicity, efficacy/PD and PK data will be received as SAS[®] datasets from the data management facility

14. Handling of Missing Data

Only observed data will be used in the data analysis except for concentration values BLQ and samples with no reportable value occurring prior to dosing as described in Section 10, 11, and 12. No attempt will be made to extrapolate or interpolate estimates for missing data.

15. Software to be Used

Efficacy/PD and PK analysis will be performed using Phoenix WinNonlin[®] version 6.4, which are validated for bioequivalence/bioavailability studies by inVentiv. The inferential statistical analyses, the safety data tables and listings, the efficacy/PD data tables and listings, the immunogenicity data tables and listings as well as PK tables and listings will be created using SAS[®], release 9.2 or a higher version. PK figures will be created using R version 3.2.2 (or

higher). The PK report text will be created using Microsoft® Office Word 2010, or a higher version.

16. Reference List

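### SAP 10.4.1 reads interference on AUEC14-t only from the vaccine-by-globulin interaction, which does not test whether SYN023 lowers the response; the ratios that would show it have no limit, and the protocol's limits are dropped without being listed

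*SAP*

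**What the plan says.** SAP 10.4 treats the trial as a 2x2 layout, 40 subjects per cell: vaccine (RVi, RVa) by immune globulin (RIG, SYN023). The second factor is called IG in some sentences and Conmed in others. Section 10.4.1 fits an ANOVA to the log-transformed areas at alpha 0.05 with both main effects and their interaction. For AUEC14-t it adds that "a statistically significant Vaccine*Conmed interaction term will be interpreted as a possible interference of RIG or SYN023 on the vaccines", and that each vaccine is then examined separately. If the interaction is not significant, "the analysis will be rerun excluding this term from the ANOVA model in order to obtain ratios and confidence intervals where appropriate".

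For AUEC0-t, AUEC14-t and Emax the reported quantity is "the ratio (RIG/SYN023) of the geometric least-squares means, calculated according to the formula" 100·e^(X−Y), with a 90% interval. The 80.00% to 125.00% requirement applies to AUEC0-t alone. Section 5 makes AUEC0-t primary and says "All other PD parameters will be regarded as secondary parameters". Section 10.4.2 gives the same ratio for each day from Day 1 to Day 112, "as well as the corresponding 90% and 95% geometric confidence intervals will be determined", with no margin. Section 12.4 adds that a table and figures "presenting RVNA on SYN023 concentrations ratios over time will be provided".

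Protocol 7.3 takes a different route: "To investigate any interference of SYN023 to the immune response generated by the vaccine, a non-inferiority test" of AUC14-last for each vaccine, using a one-sided 90% interval against 80%. It also mentions a Wilcoxon test at selected time points with a 10% margin. Both are worded as tests that can be done. The definition of pharmacodynamic efficacy, given there and in protocol 2.2, is worded as firm: besides RVNA above 0.5 IU/mL, SYN023 may be no more than 10% below RIG at any time point through Day 35.

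SAP Section 4 lists AUC14-last only as renamed and AUC0-inf as removed. It does not mention the two tests or the 10% criterion.

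**The concern.** The protocol's rationale is to find out whether 0.3 mg/kg SYN023 inhibits the response to either licensed vaccine. AUEC14-t is the parameter the protocol ties to that question. The SAP's only reading rule for it uses a contrast that is zero whenever SYN023 lowers the response by the same factor with both vaccines. The same contrast is non-zero when SYN023 raises AUEC14-t more with one vaccine than with the other.

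So the report could raise possible interference where there is none. Where there is interference, it would have a ratio and an interval but no prespecified standard for judging them. Because Section 4 shows AUC14-last only as renamed, a reader would also assume that the protocol's test on it survives.

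**Working it through.** **Inputs.** 40 per arm and alpha 0.05 (SAP 3.1, 10.4.1). Protocol 7.7 uses a CV of 15-25% for RVNA and 10-20% for AUC. I take 25% as the documented upper end; 50% and 80% are assumptions to show the range.

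**The plan's own figures.** Protocol 7.7 states power 0.838 for n = 40, SD 3 and a difference of 2. A two-sample noncentral t with noncentrality 2/(3·√(2/40)) = 2.98 at one-sided 0.025 gives 0.8376, so it reproduces. Its AUC statement (bound 0.9, over 80% power up to CV 20%) reproduces per vaccine at CV 20% only at one-sided 0.10 and a true ratio of 1 (0.861); at one-sided 0.05 it is 0.762.

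**Formulas.** Let r be the true SYN023/RIG ratio of AUEC14-t for each vaccine, and s = √ln(1+CV²) = 0.246 / 0.472 / 0.703.

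- Interaction: ln r(RVi) − ln r(RVa), SE = s·√(4/40), df 156, two-sided 0.05.
- IG effect with the interaction dropped: mean of the two ln r, SE = s·√(1/40), df 157, two-sided 0.05.
- Per-vaccine rule: ln r against ln 0.80, SE = s·√(2/40), df 156, one-sided 0.10.

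| True r (one vaccine, other vaccine) | Event | CV 25% | CV 50% | CV 80% |
|---|---|---|---|---|
| equal, any value | interaction significant | 5% | 5% | 5% |
| 0.7, 0.7 | IG effect significant | >99.9% | 99.7% | 89% |
| 1.0, 0.7 | interaction not significant | 0.5% | 34% | 64% |
| 1.0, 0.7 | IG effect significant | 99.5% | 66% | 36% |
| 1.0, 1.25 | interaction significant, nothing lowered | 81% | 32% | 17% |
| 1.0 | one vaccine passes the 80% rule | 99.7% | 80% | 55% |
| 0.7 | one vaccine passes the 80% rule | <0.1% | 0.6% | 1.7% |
| 1.0 | one vaccine, one day, passes a 10% rule (ln 0.90, one-sided 0.10) | 73% | 39% | 27% |

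The first row needs no CV: the contrast is ln r − ln r = 0, so the test rejects at its alpha. In the third row, the ratio reported after pooling has expectation √0.7 = 84%.

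**Passive antibody.** AUEC14-t also contains SYN023's own activity. Protocol Table 1.5-1 gives Phase 1 means at 0.3 mg/kg of 3.78, 2.82, 1.82 and 0.22 IU/mL at Days 14, 28, 35 and 84. Interpolating Day 42 (1.59) and assuming 0 at Day 112, the trapezoids sum to 46.2 + 16.2 + 11.9 + 38.0 + 3.1 = 115.5 Day·IU/mL over 98 days. Assume a flat vaccine RVNA of V, a vaccine response under SYN023 of f·V, and no passive activity from RIG (the documents give none). The area ratio is then [98(fV − 0.5) + 115.5] / [98(V − 0.5)].

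- V = 5, f = 0.7: (294 + 115.5)/441 = 92.9%. V = 10: (637 + 115.5)/931 = 80.8%. V = 20: 75.3%.
- A 30% cut in vaccine response then passes the 80% rule in 92% / 55% / 37% (V = 5), 14% / 12% / 11% (V = 10) and 1% / 3% / 5% (V = 20). These are upper bounds, since RIG's passive activity would lower the ratio.
- At Day 84 the ratio is (0.7V + 0.22)/V = 74%, 72% and 71%, so the cut shows.
- With V = 5 for one vaccine and 10 for the other, the interaction is significant in 43% / 15% / 10% with the cut and 32% / 12% / 8% without it. Both sets are at most 6% if RIG's passive activity equals SYN023's.

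**The case against.** The strongest reply is that the SAP does not depend on the interaction to reveal a loss. It tests the IG main effect, which has high power against a uniform 30% deficit. It reports the AUEC14-t ratio with a 90% interval and daily ratios with 90% and 95% intervals. Section 10.4 also tabulates geometric means of every PD parameter for each of the four arms, so per-vaccine point ratios can be formed whatever the interaction shows. All of this stands. A reader might infer that a uniform loss would go unnoticed, or that a null interaction will be reported as proof of no interference. The documents support neither: the loss would be visible, and the sentence says only what a significant interaction would suggest.

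A reader might also infer that a binding 80% test was dropped. The protocol makes that test and the Wilcoxon test optional; only the 10% criterion is worded as firm.

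Two further points have weight. At the documented CV of 25%, the interaction misses a 30% one-vaccine deficit in only 0.5% of trials; the larger figures rest on assumed CVs. And the 80% rule can itself pass a real cut in vaccine response when passive SYN023 makes up much of the RVNA.

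The objection does not supply a standard. The IG effect, the ratios and the per-arm means have no limit on AUEC14-t and no stated conclusion, and no per-vaccine interval exists when the interaction is not significant.

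**Conclusion.** The point holds as a gap in interpretation, not in detection, and should be fixed. The one interference rule for AUEC14-t is aimed at the wrong contrast: 5% for any proportionally equal loss, and up to 81% (CV 25%) when SYN023 is 25% higher with one vaccine and lowers nothing. That 5% follows from the definition of an interaction; the other percentages rest on log-normal data, 40 evaluable per arm and the stated CVs. The passive-antibody figures rest further on assumed vaccine RVNA levels and on unknown RIG activity, and serve only to show how a pass should be read.

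The primary AUEC0-t criterion is unaffected. It does not fill the gap, because AUEC0-t starts at Day 0 and so includes the early passive-antibody period. The unlisted loss of the 10% criterion is a separate documentation fault, since protocol 7.8.2 says changes to the planned analyses will be set out in the SAP.

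**What to change.** Replace the interaction sentence in SAP 10.4.1 with:

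> For each vaccine separately, SYN023 is non-inferior to RIG on AUEC14-t if the lower one-sided 90% confidence limit of the SYN023/RIG ratio of geometric LS means exceeds 80% (equivalently, the upper limit of RIG/SYN023 is below 125%). Both contrasts are estimated from the full Vaccine x IG model whatever the interaction p-value. The interaction is reported only as a check of consistency between vaccines.

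Add:

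> AUEC14-t includes passive antibody activity. A pass supports non-inferior total RVNA and does not exclude suppression of the vaccine response; it is read with the per-vaccine Day 84 and Day 112 ratios and confidence intervals.

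In Section 4, list and justify the removal of the Wilcoxon test and the 10% criterion, or carry the 10% criterion over with a stated decision rule. As a one-sided 90% bound per vaccine and day it would pass only 73% / 39% / 27% of the time at true equality, before requiring every day through Day 35. Also note that the 80% limit differs from the 0.9 bound used for AUC power in protocol 7.7.

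The cost is SAP wording and two contrasts from a model already fitted, plus per-vaccine contrasts at Days 84 and 112. It belongs in the SAP that protocol Section 7 requires before any unblinded preliminary review. The downside is wider intervals, 40 against 40 instead of 80 against 80: with no deficit each vaccine passes 99.7% / 80% / 55% of the time, and both pass 99% / 63% / 31%.
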